### **Sampling:**

Blood sampling: About 5.0 ml venous blood sample was taken from each patient. 2.0 ml blood was put into vacutainer Ethylene-diaminetetra-acetic acid (EDTA) tube for CBC. The reminder of blood sample was put into plain tube for serum separation and estimation of LFT, RFT, The CRP level was measured using ABX Pentra 400 (HORIBA, Germany), whereas the albumin level was measured using HumaStar 80 (HUMAN, Germany). Reference values for serum albumin is 35 to 55 g/l and for CRP is less than 6 mg/dl CLI will be calculated as CRP divided by serum albumin and multiplied by 100 in the first day post-operative and daily for 5 days with a cut-off

point  $< 85.55$  (PALACIOS et al., 2018).

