Capillary leak syndrome (CLS) refers to a syndrome of deranged fluid homeostasis, often observed in critically ill patients, CLS is frequently defined by excessive fluid shift from the intravascular to the extravascular space, resulting in intravascular hypovolemia, extravascular edema formation, and hypo perfusion necessitating further fluid resuscitation. In health, fluid exchange between intravascular and extravascular spaces is vital for maintaining the body's homeostasis. However, disturbances in this delicate equilibrium, can lead to the clinical picture of CLS (Saravi et al., 2023).

CLI is measured by dividing CRP level by albumin level. Systematic response to tissue injury, including major surgery, is marked by increased pro inflammatory cytokines, which promotes CRP production and capillary leakage. If the injury still exists, inflammatory process will continue (Susanti et al., 2021).

Our study will be done to evaluate the association between capillary leak index (CLI) and intensive care unit (ICU) related mortality in patients underwent major abdominal surgery.

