#### **Sampling Method:**

Simple randomization.

**Sample Size:** Using the PASS 15 program for sample size calculation, reviewing results from the previous study (Susanti et al, 2021) showed that the mortality rate among

the study group was 14.5%11/67) and, that the CLI at day three is a good predictor for mortality with ROC-AUC=0.892, based on these findings and after 15% adjustment for dropout rate a sample size of at least 50 patient achieves 95% power to detect a difference of 0.3920 between the area under the ROC curve (AUC) under the null hypothesis of 0.5000 and an AUC under the alternative hypothesis of 0.8920 using a two-sided z-test at a significance level of 0.050. The data are continuous responses.

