### **Study Procedures:**

All patients will be subjected to the following in the first post-operative day in the ICU:

1. Full history taking including

- Demographic Data: these include age, sex and BMI.
- Medical history: this includes diabetes mellitus (DM), cardiopulmonary diseases, renal or hepatic diseases.
- APACHE II Score.

- SOFA Score.
  2. Patients will be divided into two groups according to CLI
- Group I: Low CLI < 85.55
- Group II: High CLI > 85.55 (**PALACIOS et al., 2018**).

3. History of previous operations.
4. Drug history & special habits.
5. Complain of the patient:
  - Abdominal pain: This included onset, course, duration, site, radiation.
6. Associated symptoms: e.g.: Vomiting, change in bowel habits (constipation or diarrhea), Fever, tachycardia and tachypnea.
7. Investigations:
  - Laboratory investigations: Complete blood count (CBC). Liver function tests (LFT). Renal Function test (RFT). Coagulation profile. Daily assessment.
  - Specific laboratory investigations: CRP and Serum albumin Daily assessment.
  - Radiological investigations: Plain abdomen X-ray erect x-ray, Pelvi-abdominal ultrasonography, Computed Tomography (CT) abdomen as needed.
8. Management of sepsis and septic shock and will be done according to surviving sepsis campaign guidelines 2021.
9. Continuous monitoring of Temp, NIBP, IBP, HR, RR, intra-abdominal pressure, sPO2, UOP and GCS.

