## **Measurements**

### Primary outcome measure:

Correlation between CLI and 28 days Mortality.

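### Is the capillary leak index defined too loosely for its 85.55 cut-off to give reproducible Low and High groups?

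*Combined protocol and SAP*

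**What the plan says.** The Introduction describes the index in general terms: "CLI is measured by dividing CRP level by albumin level". It gives no multiplier and no units.

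The Sampling section of the Methodology gives the working rule: "CLI will be calculated as CRP divided by serum albumin and multiplied by 100", on the first postoperative day and daily for five days. The sentence containing it first names the analyser for each analyte and the laboratory limits: "Reference values for serum albumin is 35 to 55 g/l and for CRP is less than 6 mg/dl". It ends with the 85.55 cut-off, credited to a cited septic shock study.

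Study Procedures uses that cut-off for grouping: "Patients will be divided into two groups according to CLI", with "Group I: Low CLI < 85.55" and "Group II: High CLI > 85.55". No units accompany the number.

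The primary outcome is "Correlation between CLI and 28 days Mortality", without saying whether CLI is continuous or grouped. The sample size rests on an AUC of 0.892 against 0.5. The SAP plans ROC analysis and defines sensitivity, specificity and predictive values, but does not tie them to 85.55.

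**The concern.** A fixed threshold on a ratio has meaning on one scale only. Here the ratio is written in two ways that differ by a factor of 100. The only units on the page have different volume bases (CRP per decilitre, albumin per litre), and the cut-off is imported without its scale. A reader who takes CRP in mg/L, or who puts both analytes on the same volume base, gets a CLI ten times the printed-unit value, and many patients change group.

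At stake would be every Low/High comparison and any sensitivity, specificity or predictive value reported at 85.55. On the wrong scale almost all of the 50 or so patients would fall into one group, and the comparison would tell us nothing. The result also could not be set beside the study that supplied the cut-off.

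**Working it through.** **Inputs.** Cut-off 85.55 (Study Procedures, Sampling). Multiplier 100 and units, CRP in mg/dl and albumin in g/l (Sampling). Reference limits CRP 6 mg/dl and albumin 35 to 55 g/l (Sampling). The patient values below are assumptions. The cut-off has no derivation in the documents, so it cannot be reproduced.

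**1. Reference limits.**
- Printed units: 6/35 × 100 = 17.1 and 6/55 × 100 = 10.9. Both are Low.
- Albumin converted to g/dl: 6/3.5 × 100 = 171 and 6/5.5 × 100 = 109. Both are High.

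The second line needs a conversion that the protocol does not ask for. On the printed units a person at the laboratory limits is Low, as one would expect.

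**2. CRP needed to reach 85.55 at albumin 25 g/l.**
- mg/dl over g/l, × 100 (as printed): 85.55 × 25/100 = 21.39 mg/dl = 213.9 mg/L.
- mg/L over g/l, × 100: 85.55 × 25/100 = 21.39 mg/L.
- mg/L over g/l, no multiplier: 85.55 × 25 = 2,139 mg/L.
- mg/dl over g/l, no multiplier: 85.55 × 25 = 2,139 mg/dl = 21,388 mg/L.

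Over albumin 20 to 35 g/l, the first threshold runs from 171 to 299 mg/L and the second from 17 to 30 mg/L.

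**3. One patient, CRP 150 mg/L (15 mg/dl), albumin 25 g/l (2.5 g/dl).**
- As printed: 15/25 × 100 = 60, Low.
- CRP in mg/L over g/l, × 100: 150/25 × 100 = 600, High.
- Printed units, no multiplier: 15/25 = 0.6, Low.
- mg/L over g/dl, no multiplier: 150/2.5 = 60, Low.

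The first and last lines are algebraically the same index. The Introduction and the Sampling section can therefore agree under one choice of units, although the protocol does not state the units that the Introduction would need.

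**4. Share classed High.** Assume a median CRP of 100 to 200 mg/L with log-SD 0.6, and albumin with mean 25 and SD 5 g/l. Simulation gave 12 to 47% as printed, 99 to 100% with mg/L over g/l × 100, and about 0% with mg/L over g/l and no multiplier. As a rough hand check, treat albumin as lognormal with log-SD 5/25 = 0.2. The log-SD of CLI is then √(0.36 + 0.04) = 0.632.
- As printed, median 100: z = ln(100/213.9)/0.632 = −1.20, about 11%.
- As printed, median 200: z = ln(200/213.9)/0.632 = −0.11, about 46%.
- CRP in mg/L, median 100: z = ln(100/21.39)/0.632 = 2.44, about 99%.

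**5. What does not depend on scale.** The AUC is the probability that a patient who dies has a higher CLI than one who survives. Multiplying every CLI by the same positive constant leaves it unchanged. The same holds for correlation coefficients, and for t and Mann-Whitney tests comparing CLI between survivors and non-survivors. Only the Low/High split, and whatever is reported at 85.55, depends on scale.

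**The case for a change.** The strongest case for a change is that a rule that can be computed is not thereby a valid one. The protocol never says that the reference-range units enter the formula, and nothing confirms that the cited study derived 85.55 on that scale. If the mg/dl beside CRP is a typing slip and results are entered in mg/L, every patient between the two thresholds in step 2 changes group and the Low group nearly disappears. The primary outcome does not rule out a grouped CLI, and writing the units down would cost one line.

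Part of this stands. The definition is underspecified, the multiplier is written inconsistently, and the tenfold shift needs no distributional assumption. The documents cannot settle whether mg/dl is a slip or which scale the source used.

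The stronger claim, that formula, units and cut-off contradict one another, does not stand. The Introduction is background and cites a different study from the one that supplied the cut-off. The matched-unit reading is nowhere in the text. On the units that are there, 85.55 is reachable and gives a usable split. Within this study there is one ICU and one named analyser per analyte, so nothing suggests that conventions would be mixed between patients.

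**Conclusion.** No change to the plan follows. The Sampling section supplies one operative definition: CRP in mg/dl, divided by albumin in g/l, times 100, compared with 85.55. An analyst who follows it gets one reproducible value and one group per patient. The missing factor of 100 in the Introduction is loose background wording, and the missing units beside the formula are a detail filled from the same sentence.

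If the unit were misread, the threshold would move tenfold (214 against 21.4 mg/L of CRP at an assumed albumin of 25 g/l). That would affect the Low/High groups and any accuracy figures at 85.55. It would leave untouched the AUC on which the sample size is built and the planned ROC analysis. A misreading would also show at once, because nearly all patients would fall on one side. It could be undone, because CRP and albumin are themselves recorded daily and the index can be recalculated on any scale.

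The conclusion rests on reading the printed units as those of the formula, and on there being no evidence in the documents that the cut-off belongs to another scale. The 12 to 47% share classed High also depends on the assumed CRP and albumin distributions.

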## **Measurements**

### Primary outcome measure:

Correlation between CLI and 28 days Mortality.

### Secondary outcomes measure:

- Mechanical Ventilation days.
- Incidence of organ failure.
- Length of ICU stays.

### **Statistical Analysis:**

All data will be recorded, tabulated, analyzed and statistically compared between patients to identify any significant difference between them

The finding will be discussed with regard to the achievement of the aim, their significance and their comparison with other available data in medical literature.

# Statistical analysis Plan

## NCT Number: NCT06901544

Statistical analysis was done by SPSS v27 (IBM©, Armonk, NY, USA). Shapiro-Wilks test and histograms were used to evaluate the normality of the distribution of data. Quantitative parametric data were presented as mean and standard deviation (SD) and were analyzed by unpaired student t-test. Quantitative non-parametric data were presented as the median and interquartile range (IQR) and were analyzed by Mann Whitney-test. Qualitative variables were presented as frequency and percentage (%) and analyzed using the Chi-square test. A two-tailed P value < 0.05 was considered statistically significant.

### Evaluation of Diagnostic Performance:

a) Diagnostic sensitivity: It measures the incidence of true positive results in patients' groups.  $(TP)/(TP+FN) \times 100$ . Where:

TP (true positive): number of diseased patients accurately classified by the test and FN (false negative): number of diseased patients accurately misclassified by the test.

b) Diagnostic specificity: It measures the incidence of true negative results in a non-diseased group.  $(TN)/(TN+FP) \times 100$ . Where:

TN (true negative): number of non-diseased subjects correctly classified by the test FP (false positive): number of non-diseased patients misclassified by the test.

c) Positive Predictive value (PPV): It is the percentage of true positive results among total positive results.  $(TP)/(TP+FP) \times 100$ .

d) Negative Predictive value (NPV): It is the percentage of true negative results among total negative results.  $(TN)/(TN+FN) \times 100$ .

e) Receiver Operating Characteristic curve (ROC-curve) analysis:

The overall diagnostic performance of each test was assessed by ROC curve analysis, a curve that extends from the lower left corner to the upper left corner then to the upper right corner is considered a perfect test. The area under the curve (AUC) evaluates the overall test performance (where the area under the curve >50% denotes acceptable performance and area about 100% is the best performance

for the test). A value below 0.5 indicates a very poor model. A value of 0.5 means that the model is no better than predicting an outcome than random chance. Values over 0.7 indicate a good model. Values over 0.8 indicate a strong model. A value of 1 means that the model perfectly predicts those group members who will experience a certain outcome and those who will not.

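### The SAP's AUC scale calls anything above 50% acceptable on the point estimate, asks for no confidence interval, and is not tied to the test of AUC = 0.5 that sized the study

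*Combined protocol and SAP*

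**What the plan says.** The SAP's only guidance on reading an AUC is item e of Evaluation of Diagnostic Performance. It describes a scale "where the area under the curve >50% denotes acceptable performance", with values near 100% as best. The same item says "A value of 0.5 means that the model is no better than predicting an outcome than random chance", and calls values over 0.7 good and over 0.8 strong. No standard error, confidence interval, p-value or test accompanies any of these labels, and neither the protocol nor the SAP asks for a confidence interval anywhere.

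The protocol's sample size paragraph does have a test in mind. It sets the AUC "under the null hypothesis of 0.5000" against "an AUC under the alternative hypothesis of 0.8920", "using a two-sided z-test at a significance level of 0.050". The prior result it cites is for CLI on day three.

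The opening paragraph of the SAP says that non-parametric quantitative data "were analyzed by Mann Whitney-test" and that "A two-tailed P value < 0.05 was considered statistically significant". It does not say which groups are compared. The only groups the protocol defines are in Study Procedures, on the first post-operative day: "Patients will be divided into two groups according to CLI". The primary outcome is the relation of CLI to 28-day mortality, and CLI is calculated daily for 5 days.

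**The concern.** An AUC of 0.5 is what a useless marker gives on average, so about half of all samples from a useless marker fall above it. A scale whose lowest favourable label starts at 0.5, with no allowance for sampling error, cannot tell weak evidence from none. With few deaths the AUC is imprecise and the gap is wide: estimates well above 0.5 can be fully compatible with chance.

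The study is meant to judge whether CLI is a prognostic indicator. It therefore has to recognise a marker that does not work. A report that follows the printed scale could call CLI acceptable for predicting death when the data do not separate it from chance, and no interval would alert the reader.

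**Working it through.** **Inputs.** From the protocol's sample size paragraph: null AUC 0.5, alternative 0.892, two-sided alpha 0.05, power 95%, 15% dropout, 50 patients, and prior mortality printed as 14.5% and as 11/67 (which is 16.4%). From the SAP: the label threshold of 0.50.

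**Reproducing the plan's figure.** With D deaths and S survivors, the null standard error is SE0 = sqrt[(D + S + 1)/(12DS)]. Power = Phi[(0.392 − 1.96·SE0)/SE1], with SE1 the Hanley-McNeil standard error at 0.892. At 14.5% mortality and N = 44, SE0 = 0.125, SE1 = 0.087 and power = 0.955; N = 43 falls just short. Dropout then gives 44/0.85 = 52 or 44 × 1.15 = 51. The Obuchowski approximation gives N = 43, hence 51 or 50. The stated 50 reproduces at 14.5%, so the sample size is not at fault.

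**Number of deaths (assumption).** 50 × 0.85 = 42.5, so 42 to 50 patients are analysed. 42 × 0.145 = 6.1 and 50 × 11/67 = 8.2, so about 6 to 8 deaths are expected. Ten to 20 deaths in 50 are shown for a sicker cohort.

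**What the sizing test requires.** The Mann-Whitney statistic is U = D·S·AUC, so a Mann-Whitney test of CLI by survival status is a test of AUC = 0.5. The exact null distribution without ties gives the middle four columns below. The last column is the Hanley-McNeil interval, 0.60 ± 1.96·SE.

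| Deaths / survivors | Useless CLI: P(AUC > 0.5) | Smallest significant AUC | Useless CLI: above 0.5, not significant | Two-sided p at AUC 0.60 | 95% CI at AUC 0.60 |
|---|---|---|---|---|---|
| 6/36 | 0.493 | 0.755 | 0.469 | 0.449 | 0.34–0.86 |
| 7/43 | 0.500 | 0.734 | 0.476 | 0.410 | 0.36–0.84 |
| 8/42 | 0.495 | 0.723 | 0.471 | 0.382 | 0.38–0.82 |
| 10/40 | 0.495 | 0.702 | 0.470 | 0.344 | 0.40–0.80 |
| 15/35 | 0.500 | 0.678 | 0.476 | 0.274 | 0.42–0.78 |
| 20/30 | 0.496 | 0.667 | 0.472 | 0.241 | 0.44–0.76 |

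Hand check at 7/43: SE0 = sqrt[51/(12 × 301)] = 0.119, so the threshold is 0.5 + 1.96 × 0.119 = 0.733. At AUC 0.60, z = 0.10/0.119 = 0.84 and p = 0.40.

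The test rejects upward for a useless CLI in 2.4% to 2.5% of studies across the table.

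**If CLI has some value.** A binormal simulation (40,000 draws) gave the share of studies with an AUC above 0.5 that is not significant. At a true AUC of 0.60 it was 66% to 68%. At 0.892 it was 4.2%, 2.2% and 1.1% with 6, 7 and 8 deaths, and under 0.5% with 10 to 20.

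**Why one day must be named.** The 2.4% to 2.5% holds for a single test. For a useless CLI at 7/43 tested on five days, a simulation (20,000 draws, assumed equal between-day correlation) found an upward rejection on at least one day in 6.3% of studies at correlation 0.8 and 9.1% at 0.5.

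**Why the test should govern, not the lower confidence limit.** In a null simulation (20,000 draws) the lower limit of a DeLong Wald interval lay above 0.5 in 4.8% of studies with 6 deaths and 3.0% with 20, against a nominal 2.5%.

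**The case against.** The strongest reply is that the phrase is a gloss in a parenthesis, within a set of textbook definitions. The SAP nowhere says that CLI will be declared a predictor if the AUC exceeds 0.5, and its one inferential rule is the two-tailed P < 0.05. This stands: a reader might infer a decision rule, but the text supports only an interpretive label that is not connected to any test.

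A reader might also infer that the test against 0.5 was abandoned. The documents do not show that. The protocol's sizing statement is never withdrawn, and the Mann-Whitney test would serve if applied to CLI by survival status. That grouping is natural given the primary outcome, and comparing CLI between CLI-defined groups would be circular. But the SAP does not state the grouping, and it would send CLI to a t-test if CLI looked normal. The link is possible, not specified.

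The same item says that 0.5 is chance and keeps *good* for values over 0.7. A useless CLI passes 0.7 in only 6.0% of studies with 6 deaths, 3.7% with 8 and 0.8% with 20. That limits the point to the lowest label. The 0.7 band conflicts with the test only at about 6 to 8 deaths.

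Finally, the figure of one half follows from the symmetry of the null distribution and would arise in any trial. That is true, and it is the reason why 0.5 cannot serve as a favourable threshold.

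**Conclusion.** The point holds as a defect in the interpretation scale and should be corrected. Used as written, the label would call a CLI without predictive value acceptable or better in 49% to 50% of studies, and in about 47% it would do so without a significant difference from 0.5. These are mislabelling rates. Reading them as the study's type I error would be wrong, because the SAP does not make the label its criterion for a claim and keeps P < 0.05 alongside it.

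The result for a useless marker hardly depends on the number of deaths. The p-values and intervals at an AUC of 0.60 do depend on it, and the range of 6 to 20 is an assumption. The exact figures assume no ties, the Hanley-McNeil intervals are rough at 6 to 8 deaths, and the rates at true AUCs of 0.60 and 0.892 assume a binormal model. If CLI performs as the sizing supposes, little is lost. The wording matters if CLI is weak or useless.

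**What to change.** In the SAP, Evaluation of Diagnostic Performance, item e:

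- Delete the wording that makes an AUC above 50% acceptable.
- Report the AUC of CLI for 28-day mortality with a 95% CI, and name the method.
- State that the conclusion rests on one pre-specified test: the two-sided 0.05 Mann-Whitney test of CLI by 28-day survival status, whatever the normality check shows, on one named day. Day three matches the sizing. CLI is called predictive only if this test rejects in favour of an AUC above 0.5.
- Report AUCs for the other days with CIs as secondary.
- Keep the 0.7 and 0.8 labels as descriptive terms beside the CI.

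This costs a few sentences and one more ROC output. It needs no extra patients or data, and the SAP already names the test. There are two downsides. The verdict will be less favourable when the AUC is imprecise. The CI and the test can also occasionally disagree near 0.5, so the SAP must say that the test governs.
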